6.2.1.2 Prohibited Therapy

Use of the following therapies is not permitted from the day of Screening until completion of the Post-treatment period:

- Platelet preparations (except for use prior to the invasive procedure and as rescue therapy). Note that patients who receive a platelet transfusion prior to the invasive procedure (based on the determination of platelet count pre-operatively) may receive subsequent platelet transfusions.
- Blood preparations and alternatives to blood, except for platelet preparations, red blood cell preparations, and albumin preparations (eg, whole blood cell preparations; human immunoglobulin preparations other than those targeting specific infections, such as antitetanic globulin and hepatitis B immune globulin; coagulation factor products; fibrinogen other than fibrinogen for tissue adhesion; antithrombin III; fresh frozen plasma; and recombinant coagulation factor product) unless needed as rescue therapy for bleeding
- Anticancer drugs, except for those used in patients in whom the primary invasive procedure is TACE or lipiodolisation, and patients in whom the primary invasive procedure is liver ablation/coagulation with TACE or lipiodolisation planned after completion of study assessments on Day 8
- Interferon products
- Macrophage colony-stimulating factor (M-CSF) products
- Granulocyte CSF (G-CSF) products
- Erythropoietin
- TPO receptor agonists other than the study drug
- Antithrombotic agents (heparin, aspirin, dipyridamole, ticlopidine, urokinase, etc.) except for use as rescue therapy
- Desmopressin products
- Monoethanolamine oleate
- Other investigational products
- Radiotherapy
- Exsanguination
- Any invasive procedures except for the primary invasive procedure in the study

The following therapies can be concomitantly used after assessment on Day 8 provided

that the primary invasive procedure is liver ablation/coagulation:

- TACE
- Lipiodolisation with anticancer drugs (ie, Lip-TAI)
- transcatheter arterial embolisation (TAE) excluding Lipiodol infusion for marking

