7.4 Invasive Procedures

The planned invasive procedure will be performed in the Post-treatment period between Days 9 and 14. The need for the invasive procedure will be reassessed in the event of the following:

- Platelet count $\geq 200 \times 10^9/L$
- Administration of an antithrombotic drug
- In the opinion of the investigator, the procedure is no longer in the patient's best because of an AE or other concern
- The patient requests cancellation of elective procedure after randomisation

If any of the above criteria are met and the elective procedure cannot be performed between Days 9 and 14, it may be performed up to Day 35 of the study. If a patient does not undergo a procedure, all relevant follow-up assessments should be performed and data should be collected up to Day 35. In case the invasive procedure performed between Days 9 and 14 needs to be repeated, the same procedure may be performed after Day 15 according to the discretion of the investigator.

Information on whether to perform the planned invasive procedure, details of the procedure performed (eg, percutaneous radiofrequency ablation [RFA]/microwave coagulation therapy [MCT], laparoscopic RFA/MCT, endoscopic variceal ligation [EVL], endoscopic injection sclerotherapy [EIS], TACE, TAE, or other), the date performed, the initiation time of the procedure, and whether the procedure was performed within the specified period will be recorded on the CRF. If the planned invasive procedure is not performed within the specified period or is not performed at all, the reason will be recorded on the CRF.

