Appendix 4: List of Example Invasive Procedures

Region	Type of Surgery
Liver	
radiofrequency ablation (RFA)percutaneous microwave coagulation therapy (PMCT)percutaneous ethanol injection therapy (PEIT)transcatheter arterial embolisation (TAE)/transhepatic arterial infusion (TAI)/transcatheter arterial chemoembolisation (TACE)endoscopic ultrasound-guided fine needle aspiration (EUS-FNA)laparoscopic radiofrequency ablation (LRA)laparoscopic microwave coagulation (LMC)
Biliary-pancreas	
endoscopic metallic stenting (EMS)endoscopic sphincteropapillotomy (EST)endoscopic papillary balloon dilatation (EPBD)endoscopic ultrasound-guided fine needle aspiration (EUS-FNA)
Gastrointestinal tract	
endoscopic polypectomyendoscopic submucosal dissection (ESD)endoscopic mucosal resection (EMR)percutaneous endoscopic gastrostomy (PEG)endoscopic variceal ligation (EVL)endoscopic injection sclerotherapy (EIS)endoscopic ultrasound-guided fine needle aspiration (EUS-FNA)
Urinary system	
transurethral resection of the bladder tumour (TURBT)transurethral ureterolithotripsy (TUL)
Other regions	
percutaneous needle biopsylaparoscopyarthroscopic surgeryendoscopy with possible biopsyvarious paracentesestooth extraction

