9.1 Primary Endpoint

The primary endpoint is the proportion of patients who require no platelet transfusion prior to the primary invasive procedure and no rescue therapy for bleeding from the date of randomization until 7 days after the primary elective procedure. The patients will be determined as a success for the primary endpoint if all of the following conditions are satisfied:

- Patients received no platelet transfusion from the date of randomization through at least 7 days after the primary invasive procedure (i.e., the first invasive procedure in the study)
- Patients received no rescue therapy for bleeding (including any of the following) from the date of randomization through 7 days after the primary invasive procedure
 - Platelet preparations
 - Other blood preparations, including red blood cells and plasma
 - Volume expanders
- Patients underwent an invasive procedure

In contrast, the following patients will be considered as failures for the primary endpoint if any of the following conditions is satisfied:

- Patients received at least one platelet transfusion prior to the primary invasive procedure
- Patients received at least one rescue therapy for bleeding from the date of randomization through 7 days after the primary invasive procedure
- Patients withdrew from the study before undergoing the primary invasive procedure
- Patients did not undergo an invasive procedure

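### SAP 9.1 takes the first invasive procedure as the primary one, so a permitted embolisation before a planned liver ablation can become the anchor of the primary endpoint

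*SAP*

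**What the plan says.** - **SAP 9.1** explains the term primary invasive procedure as "i.e., the first invasive procedure in the study". Success needs three things: no platelet transfusion from randomisation until at least 7 days past that procedure, no rescue therapy for bleeding up to 7 days past it, and having had an invasive procedure (indefinite article). The failure list covers transfusion before the primary procedure, rescue in the window, withdrawal before the procedure, and having no invasive procedure.
- **Protocol 6.2.1.2** prohibits "Any invasive procedures except for the primary invasive procedure in the study". It then makes an exception: "The following therapies can be concomitantly used after assessment on Day 8 provided" that the primary procedure is liver ablation/coagulation. The exception covers TACE, Lip-TAI, and TAE other than Lipiodol infusion for marking. Its anticancer-drug item describes the same patients as those in whom "the primary invasive procedure is liver ablation/coagulation with TACE or lipiodolisation planned after completion of study assessments on Day 8".
- **Protocol 7.4**: "The planned invasive procedure will be performed in the Post-treatment period between Days 9 and 14". If a reassessment criterion is met and those days cannot be kept, "it may be performed up to Day 35 of the study".
- **Protocol Appendix 4** lists TAE, TAI and TACE among the liver procedures. **SAP 9.1.1.1** has TACE and TAE as categories of the primary procedure received.
- **SAP 6.3** also ties the post-procedure visit for the bleeding scale, portal vein thrombosis and portal flow to the first procedure.

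**The concern.** The protocol names the ablation as the primary procedure when an embolisation is added. The SAP picks whichever invasive procedure comes first. Nothing in either document places the embolisation after the ablation, and nothing excludes it when the first procedure is identified. If it does come first, the two documents point to different procedures in the same patient.

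The endpoint is meant to capture transfusion before the planned elective procedure and rescue for bleeding after it. If the clock starts at the embolisation, part of the post-ablation period drops out, the meaning of a transfusion before the procedure changes, and the requirement to have had the procedure can be met without the ablation.

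**Working it through.** No stated figure is in dispute. As background, the 99% power in SAP 4.3 (100 per arm, 20% against 70%, two-sided 0.05) reproduces: the pooled-variance normal approximation gives more than 99.99%.

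**Inputs.** Let *t* be the embolisation day (Day 8 or later, after that day's assessment) and *a* the ablation day, with *a* > *t*. On schedule, *a* is between 9 and 14 (Protocol 7.4).

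**Window end.** The SAP rule, read literally, ends the window on Day *t* + 7. An ablation anchor ends it on Day *a* + 7. The post-ablation days lost are *a* − *t*, up to a maximum of 7.

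**1. Rescue, both procedures on Days 8 to 14.** There are 6 + 5 + 4 + 3 + 2 + 1 = 21 ordered day pairs.

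| Embolisation | Ablation | SAP window ends | Ablation window ends | Days lost |
|---|---|---|---|---|
| Day 8 | Day 9 | Day 15 | Day 16 | 1 |
| Day 8 | Day 14 | Day 15 | Day 21 | 6 (Days 16 to 21) |
| Day 13 | Day 14 | Day 20 | Day 21 | 1 |

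The range over all 21 pairs is 1 to 6 days. Six is the maximum and arises in one pair only.

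**2. Transfusion between embolisation and ablation, on schedule.** In all 21 pairs *a* ≤ *t* + 7, so the transfusion lies inside the SAP window and the first success condition fails. It is not a transfusion before the SAP's primary procedure, however, because it follows the embolisation. Unless it was rescue therapy, it meets no listed failure condition. SAP 9.2.1 classes everyone who is not a success as a failure; SAP 9.1 has no such sentence.

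**3. Transfusion before a postponed ablation.** It is missed only if it comes after Day *t* + 7, which requires *a* ≥ *t* + 8. With *t* = 8, that means an ablation on Day 16 or later. For example, with embolisation on Day 8, transfusion on Day 19 and ablation on Day 20, the window closed on Day 15. With no other event, the patient counts as a success.

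**4. Cancelled ablation.** The embolisation alone can meet the SAP's third success condition. Protocol 8.9.1 uses the definite article when it fails patients who did not have the procedure. SAP Section 13 lists no change on this point.

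**Size.** One patient in an arm of 100 is 1/100 = 1 percentage point. The number of patients at risk is not in the documents, so the following ranges are assumptions. Let a share *s* of all patients (10% to 50%) have an earlier embolisation, and let a fraction *f* of their failures (5% to 20%) be relabelled as successes in both arms. With *x* = *s* × *f*, the rates become 0.70 + 0.30*x* and 0.20 + 0.80*x*, a difference of 0.50 − 0.50*x*.

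- *s* = 10%, *f* = 5%: *x* = 0.005, difference 49.75 points.
- *s* = 50%, *f* = 20%: *x* = 0.10, difference 45.0 points.

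Power stays above 99.9% throughout.

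**The case against.** The best defence is that the intent is clear. Protocol 6.2.1.2 names the ablation as primary and calls the embolisations concomitantly used therapies. SAP 8.3 summarises concomitant therapy separately, and the SAP presents itself as detailing the protocol's analyses. Protocol 7.4 allows the same procedure to be repeated after Day 15, so the word first may only separate the initial performance from a repeat. TACE and TAE would appear as subgroup categories anyway, because either can be the planned procedure. A blinded case review also looks at data affecting the efficacy endpoints (Protocol 9.8.1).

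This is a plausible account of what was meant, and it limits how far the point can be pushed. It does not remove it: neither document says that an embolisation under 6.2.1.2 is left out when the first procedure is identified. None of the three sensitivity analyses in SAP 9.1.2 changes the anchor. The whole-study transfusion and rescue summaries would show the events but would not correct the primary classification.

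Some stronger readings are tempting but unsupported:

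- *That a whole randomisation stratum is affected.* Liver ablation is one level of a factor that spans two of the four CMH strata. Only patients in it with an earlier embolisation are exposed.
- *That pre-ablation transfusions generally escape.* On schedule they still block success; escape requires a postponed ablation.
- *That six lost days is typical.* It is the maximum.
- *That embolisation before ablation is planned or common.* The documents only leave the order open.

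**Conclusion.** The point holds as a defect in the written endpoint rule. Applied literally, SAP 9.1 can anchor the primary endpoint on an embolisation that the protocol treats as an addition to the primary procedure. The consequences are those in steps 1 to 4 of the working. They rest on two conditions: the embolisation precedes the ablation, and it is counted as an invasive procedure. The second follows from Protocol Appendix 4 but may not have been intended.

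A reader might infer that the trial's main comparison is unsafe. The documents do not support that: under the assumed ranges the planned difference stays between 45.0 and 49.75 points. The issue is classification, patient by patient, in the primary endpoint. It should be settled before unblinding, because afterwards the choice of anchor could be made with knowledge of the result.

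**What to change.** Amend the SAP wording as follows:

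1. Define the primary invasive procedure as the first performance of the planned procedure recorded on the CRF, or of the procedure done in its place if it was substituted. The stratification factor alone will not serve, because it separates only ablation/coagulation from other.
2. State that TACE, Lip-TAI or TAE given under Protocol 6.2.1.2 alongside a planned ablation is concomitant therapy and not the primary procedure.
3. Make success depend on the primary procedure having been done, not on any invasive procedure.
4. Count any platelet transfusion before the primary procedure as failure.
5. Use the same anchor for the post-procedure visit in SAP 6.3.
6. Keep the first-procedure anchor as a sensitivity analysis.

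The cost is SAP text and programming. The planned procedure (Protocol 7.2.7) and the procedure performed, with its date and start time (Protocol 7.4), are already collected. The sample size does not change, and nothing about which therapies may be given, or when, is altered.

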9.1.1 Primary Analysis

The number and proportion of patients who required no platelet transfusion prior to the primary invasive procedure and no rescue therapy for bleeding from the date of randomization through 7 days after the primary elective procedure will be calculated by treatment group. The primary endpoint will be presented along with 95% confidence intervals (CIs), which will be calculated with the Clopper-Pearson method.

The proportion of patients who required no platelet transfusion in the S-888711 group will be compared with that in the placebo group using the Cochran-Mantel-Haenszel (CMH) test adjusted by the stratification factors, i.e., the four strata:

- Platelet count at randomization $< 35 \times 10^9/\text{L}$ and liver ablation/coagulation
- Platelet count at randomization $< 35 \times 10^9/\text{L}$ and other invasive procedure
- Platelet count at randomization $\geq 35 \times 10^9/\text{L}$ and liver ablation/coagulation
- Platelet count at randomization $\geq 35 \times 10^9/\text{L}$ and other invasive procedure.

In addition, the differences in the primary endpoint and its 95% CI using Wald method (see [Appendix 3](#)) will be calculated.

9.1.1.1 Subgroup Analysis

The primary endpoint will be analyzed separately for the following subgroups:

- Platelet count at baseline: $< 35 \times 10^9/\text{L}$, $\geq 35 \times 10^9/\text{L}$
- Received primary invasive procedure: Percutaneous RFA/MCT, Laparoscopic RFA/MCT, EVL, EIS, TACE, TAE, other, and not performed
- Sex: male, female
- Age: < 65 years, ≥ 65 years
- Baseline body weight: $< 75 \text{ kg}$, $\geq 75 \text{ kg}$
- Race: White, NonWhite
- Child-Pugh class: A, B, C

The number and proportion of patients will be calculated by treatment group. The proportion of patients will be reported and will be compared between the S-888711 and placebo groups by Fisher's exact test. In addition, the interaction between subgroup (except received invasive procedure and Child-Pugh class C) and treatment group will be tested with Breslow-Day test.

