8.2 Rationale for Target Sample Size and Stratification Factors

Two hundred patients with CLD and thrombocytopenia who are scheduled to undergo elective invasive procedures will be randomised into either of two treatment groups (100 patients per group).

In the phase 3 study (Study 1304M0631) conducted in Japan, the proportion of patients who required no platelet transfusion prior to the primary invasive procedure was 79.2% in S-888711 3 mg group for up to 7 days and 12.5% in the placebo group. The difference of proportion of patients was 66.7% and its 95% confidence interval (CI) was [51.9%, 81.5%]. Based on the results, it was assumed that the difference in the primary endpoint to be obtained in this study is 50% between S-888711 and placebo groups. Assuming that the proportion of patients who meet the primary endpoint is 20% in the placebo group and 70% in the S-888711 group, 100 patients per arm will provide 99% power to detect a difference of 50% between S-888711 and placebo groups at a two-sided significance level of 0.05.

With 100 patients per arm, from the safety point of view, the sample size will assure at least 95% probability to detect an AE with an incidence of 3% or more.

Since the risk of bleeding is different for each elective procedure, primary invasive procedure has been selected as a stratification factor as per the phase 3 Japanese study (Study 1304M0631). Furthermore, in the Japanese study, the proportion of patients in the 3 mg group who received no platelet transfusion prior to the primary invasive procedure was relatively low in the group whose platelet count at baseline was $< 35 \times 10^9/L$ (57.1%, 4/7 patients) compared to the group whose platelet count at baseline was $\geq 35 \times 10^9/L$

(82.9%, 34/41 patients). Thus, for the current study, platelet count at baseline has been selected as an additional stratification factor

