8.9 Endpoints

8.9.1 Primary Endpoint

The primary endpoint is the proportion of patients who require no platelet transfusion prior to the primary invasive procedure and no rescue therapy for bleeding from randomisation through 7 days after the primary elective procedure. The following patients will also be considered as failures for the primary endpoint:

- Patients who withdrew from the study before receiving the primary invasive procedure
- Patients who did not receive the invasive procedure

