4.2 Study Blinding and Randomization

The study will be conducted in a double-blind manner using a placebo matching the active drug in appearance, labelling and packaging. An IVRS/IWRS will be used for central patient randomization and study drug assignment. IVRS/IWRS will assign drug identifiers according to a randomization schedule. Only an unblinded Contract Research Organization (CRO) or designee will have the authority to assign the drug identifiers. All patients, the investigator, all study personnel, and data analysts will be blinded to the

treatment assigned at randomization until database lock. The randomization schedule will be kept confidential and will not be accessible to anyone until unblinding, except for Drug Supply Management staff, IVRS/IWRS Clinical Coordinator(s), IVRS/IWRS vendor staff, unblinded statistician on the Independent Safety Committee, and for reporting suspected unexpected serious adverse reaction (SUSAR) as required by local regulation.

Eligible patients will be randomized to one of the two treatment groups (S-888711 3 mg/day for up to 7 days, or placebo for up to 7 days) in a ratio of 1:1. Randomization will be stratified by the primary invasive procedure and the platelet count at baseline as follows:

- Primary invasive procedure: liver ablation/coagulation or other invasive procedures
- Platelet count at baseline: $< 35 \times 10^9/\text{L}$ or $\geq 35 \times 10^9/\text{L}$

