7.2 Demographic and Baseline Characteristics

Demographics and baseline characteristics shown in [Table 2](#) will be tabulated by treatment group for the ITT population. Summary statistics will be calculated for continuous variables, and the frequency and proportion of patients in each category will be obtained for categorical variables.

Table 2 Demographic and Baseline Characteristics

Continuous Variable	age, height, weight, BMI, platelet count at baseline
Categorical Variable	sex, race, ethnicity, presence or absence of any transfusion history, presence or absence of history of CLD due to: - hepatitis B, - hepatitis C, - alcoholic hepatitis, - non-alcoholic hepatitis, - autoimmune hepatitis, Child-Pugh class, WHO Bleeding Scale, planned invasive procedure (liver ablation/coagulation, other), platelet count at baseline ($< 35 \times 10^9/L$, $\geq 35 \times 10^9/L$), platelet count at randomization ($< 35 \times 10^9/L$, $\geq 35 \times 10^9/L$) ECOG performance status, presence or absence of gastro oesophageal varices, presence or absence of splenomegaly, presence or absence of ascites

Details of medical history will be summarized by treatment group. The reported medical history terms will be coded using the Medical Dictionary for Regulatory Activities (MedDRA) Version 18.0 or higher.

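### Procedure type is examined only by the procedure received, with an untestable not-performed level; the planned procedure used to stratify randomisation is not a subgroup

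*SAP*

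**What the plan says.** SAP 9.1.1.1 lists seven subgroup variables for the primary endpoint. The only one concerning procedure is "Received primary invasive procedure: Percutaneous RFA/MCT, Laparoscopic RFA/MCT, EVL, EIS, TACE, TAE, other, and not performed". For every subgroup, the success proportion "will be compared between the S-888711 and placebo groups by" Fisher's exact test, and no level is exempted. The interaction rule reads: "the interaction between subgroup (except received invasive procedure and Child-Pugh class C) and treatment group will be tested with Breslow-Day test".

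SAP 9.1 counts as failures those meeting the condition "Patients did not undergo an invasive procedure". Protocol 8.9.1 does the same: "Patients who did not receive the invasive procedure".

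The procedure planned at entry is handled separately. SAP 4.2 makes it one of two stratification factors: "Primary invasive procedure: liver ablation/coagulation or other invasive procedures". Protocol 8.2 gives the reason: "Since the risk of bleeding is different for each elective procedure, primary invasive procedure has been selected as a stratification factor". The factor helps define the four CMH strata in SAP 9.1.1, and Table 2 in SAP 7.2 tabulates "planned invasive procedure (liver ablation/coagulation, other") at baseline. It does not appear in the subgroup list. SAP section 13 does not mention the point.

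**The concern.** A subgroup comparison has the protection of randomisation when membership is fixed before treatment starts. Procedure received is not fixed then. Protocol 7.4 has the need for the procedure reassessed after a platelet count of 200 × 10⁹/L or more, after an antithrombotic drug, or because of an adverse event. The study drug raises platelet counts, so whether a patient falls in a named level or in not-performed can depend on the arm.

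Two things follow. The not-performed level is a tested comparison with no possible content, and the remaining levels compare patients selected after randomisation. Meanwhile the baseline version of the same variable, already used to randomise and to adjust, gets no effect estimate by level and no interaction test. The other stratification factor fares better: baseline platelet count, cut at the same 35 × 10⁹/L, is a subgroup with an interaction test. What is at stake is a pre-specified, randomised look at whether the effect is consistent between liver ablation/coagulation and other procedures.

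**Working it through.** **1. The plan's own figure.** SAP 4.3 assumes 20% versus 70% with 100 per arm at two-sided 0.05 and states 99% power. With the pooled-variance normal approximation:

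- z = (|p₁ − p₂|√n − 1.96√(2p̄(1 − p̄))) / √(p₁(1 − p₁) + p₂(1 − p₂)), with p̄ = 0.45
- z = (0.5 × 10 − 1.96 × √0.495) / √0.37 = (5 − 1.379) / 0.608 = 5.95
- Power is above 99.99%, so the stated 99% is met. This point does not depend on it.

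**2. The not-performed level.** Every patient in it is a failure, so its table has zero successes in both arms. Fisher's exact test on (active/placebo) sizes of 1/1, 3/3, 5/5, 10/5, 5/10, 10/2 and 15/5 gives p = 1.0 each time. This follows from the endpoint definition, whatever the drug does.

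**3. Effect on the other levels taken together.** If a share q of an arm has no procedure and its success rate among all randomised is r, success among those with a procedure is r/(1 − q). Rates of 70% and 20% are from SAP 4.3. The shares q are assumptions, since the documents give none.

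| No procedure, active/placebo | Active | Placebo | Difference |
|---|---|---|---|
| 0% / 0% | 70.0% | 20.0% | 50.0 points |
| 5% / 5% | 73.7% | 21.1% | 52.6 |
| 10% / 10% | 77.8% | 22.2% | 55.6 |
| 10% / 5% | 77.8% | 21.1% | 56.7 |
| 15% / 5% | 82.4% | 21.1% | 61.3 |
| 5% / 15% | 73.7% | 23.5% | 50.2 |

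With equal success of 45% in both arms among all randomised (also assumed), shares of 10%/5% give 0.45/0.90 − 0.45/0.95 = 2.6 points, and 15%/5% give 0.45/0.85 − 0.45/0.95 = 5.6 points. Those differences come from the grouping alone.

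**4. Can the received levels stand in for the planned factor?** Only roughly. Patients without a procedure lose their planned category. Percutaneous ethanol injection, listed in Protocol Appendix 4, has no level of its own, and the documents do not say whether it counts as ablation/coagulation.

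**5. What the planned factor would offer.** It has two levels set before treatment, every randomised patient stays in one of them, and a Breslow-Day test can be run. Level sizes are not stated. For illustration, Fisher power at 70% versus 20% is 24%, 43%, 85%, 97% and 99.6% with 5, 10, 20, 30 and 40 patients per arm in a level (assumed sizes).

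**The case against.** The case for leaving the plan alone is reasonable. The primary CMH test already adjusts for planned procedure, and Appendix 3 computes a difference in each of the four strata on the way to the adjusted estimate. Subgroups lie outside the gatekeeping sequence. Protocol 8.10 plans no subgroup analysis, so the SAP breaks no commitment. The not-performed row accounts for all ITT patients, and a p-value of 1 on 0% versus 0% is unlikely to mislead anyone. If one planned level turns out small, the added subgroup may say little.

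These points limit the weight. They do not answer the omission: adjustment yields one pooled result, and SAP 9.1.1 does not say that the stratum differences will be reported or compared.

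Four stronger readings are tempting, and the documents do not support them:

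- *The trial stratified so that it could report effects by procedure.* Protocol 8.2 cites differing bleeding risk and the precedent of the Japanese phase 3 study. It does not mention subgroup reporting.
- *The trial cannot show whether the effect holds by procedure type.* The factor will be in the data. The plan simply does not commit to the analysis.
- *Platelet response determines which type of procedure a patient receives.* Protocol 7.4 shows routes by which response or treatment can affect whether or when a procedure occurs. It gives none by which response changes the type. Nor is a low count listed as a reason to cancel; Protocol 3.1 links it to transfusion.
- *An interaction claim rests on a post-randomisation variable.* The SAP excludes procedure received from the Breslow-Day test.

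**Conclusion.** The point holds as a modest, free improvement. SAP 9.1.1.1 groups by a post-randomisation variable, applies Fisher's test to a level that is 0% versus 0% by definition, and takes those failures out of the other levels. Excluding that variable from the interaction test is right, but leaves procedure type with none. As a result, the plan contains no pre-specified randomised assessment of consistency across procedure types.

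The emptiness of the not-performed comparison is certain from the endpoint definition. The size of the shift elsewhere is not known: it runs from 0.2 to 11.3 points above the planned 50 over the non-zero shares tried, all of them assumed. Precision within the planned levels is also unknown. The primary result, the type I error rate and the trial's power are untouched.

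**What to change.** In SAP 9.1.1.1:

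- Add planned primary invasive procedure, in its two categories as recorded at randomisation, to the subgroup list. Report success rates by treatment group with Fisher's test, as for the other subgroups.
- Include this factor in the Breslow-Day interaction test.
- Keep procedure received as a descriptive table without tests, with not-performed shown only as a count per arm.

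The cost is a few lines of SAP text and one extra table. The factor is already captured at randomisation and used in the CMH strata, so no new data are needed. The change should be made before unblinding.
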